9.4 STOOL COLLECTION INSTRUCTIONS FOR STUDY PERSONNEL

- Inform the participants of the following:
 - 1. Refer to "Stool Collection Instructions for Participants" for detailed instructions
 - 2. Use the kit provided to collect sample
 - 3. All Day 1, 7, 14, 21 and 30 stool samples must be frozen immediately
 - 4. Make sure to use gloves when handling sample
 - 5. Write the collection time and date on the label provided
 - 6. Call the study personnel after collecting the sample to schedule a pick up
- Make sure all caps are tightly closed when collecting sample
- Use the cooler/coolly packs when transporting sample from participant's house to Georgetown University.
- Fill out Sample Collection Form
- Before placing the sample in the freezer, make sure:
 - 1. Any names on the samples are crossed out
 - 2. Write correct Study IDs

9.5 STOOL COLLECTION INSTRUCTIONS FOR PARTICIPANTS

Stool is to be collected from your child on Days 1, 7, 14, 21 and 30.

At enrollment and throughout the study, you will be provided with stool collection materials. This kit will include: disposable gloves, 3 stool containers/vials, small plastic zipper bags, 1 large plastic zipper bag, labels and a stool collection device (a "stool hat" – if your child is toilet trained). Before you begin the collection, please clear a space or shelf in your freezer to store the samples without contact with food or other items in the freezer.

[figure not shown]
At the time of stool collection:

- 1. Wash your hands.
- 2. Put on disposable gloves.
- 3. You will be provided with labels. Please write your child's STUDY ID number (if not already on the label) and the date and time the stool was collected. Do this on the label of the 3 stool containers (vials) and once on the label on the plastic zipper bag. Please do not write your child's name on the labels.
- 4. If your child is toilet trained: Lift the toilet seat. Align the "stool hat" with the rear of the toilet rim (see Photo A). Replace the seat. Have your child use the toilet as s/he normally would, letting the stool collect in the "hat".

*Skip previous step if your child uses diapers: collect stool directly from diaper.

- 5. Unscrew the cap from one of the two smaller vials that contains liquid. Use the spoon attached at the end of the cap of vial to fill the container to the fill line indicated on the vial (but do not overfill; see Photo B).
- 6. Screw the cap back onto the container. Make sure the cap is tightly closed. Shake the vial gently until the stool is thoroughly mixed with the liquid. **Repeat** the same action for the second smaller vial with the liquid.

- 7. For the last container (the larger vial without liquid), simply collect stool to the fill line on the vial using the attached spoon and screw the cap back onto the container.
- 8. Discard remaining stool into the toilet and flush. Discard diaper or stool hat.
- 9. Place the containers/vials into the small plastic zipper bag and seal the bag. Then place the small bag into the large plastic zipper bag. Seal the bag.
- 10. Place the sealed plastic zipper bag into the **FREEZER immediately** for storage.
- 11. Discard gloves and wash your hands.
- 12. Contact the research personnel as soon as possible to arrange a time for stool collection pickup, which should typically occur within 24-48 hours.

Please avoid contact with the liquid preservative in the stool containers. If any of the liquid comes into contact with skin or eyes, wash thoroughly with water. Do not ingest/drink the preservative.

[figure not shown]

Photo B

10 ASSESSMENT OF SAFETY

We will protect participants by alerting the parents/caregivers of the common reactions to yogurt and by listing common reactions for them to monitor. We will also have close follow-up and 24-hour phone line accessibility there is a question of an allergic or idiosyncratic reaction.

Details of all adverse events reported by parents/caregivers or observed by research personnel will be recorded in the adverse event report forms. All adverse events observed will be recorded separately and all will be reported to the IRB on IRB Adverse Event forms.

In order to prevent the occurrence of adverse events, we will be stringent in enforcing our exclusion criteria, paying particular attention to the potential for an allergic reaction to strawberry or yogurt on the part of the participant.

Any child who develops evidence of allergy or hypersensitivity to any component of the investigational product will be withdrawn from the clinical study and receive no further doses of either drink. We will continue to follow these participants for safety for the remainder of the study.

10.1 ADVERSE EVENTS

An adverse event (AE) refers to any untoward medical occurrence in a clinical investigation subject administered an investigational product and which does not necessarily have a causal relationship with the treatment. An AE can therefore be any unfavorable and unintended sign, symptom, or disease temporally associated with the use of the investigational product, whether or not considered related to the product. This includes events not present at the start of the study or worsening during the course of the study even if present at the study start. An AE can be reported anytime after study enrollment; a participant is considered enrolled once the informed consent form is signed by the parent/caregiver.

Details of all solicited and unsolicited adverse events reported by parents/caregivers or observed by research personnel must be recorded in the adverse event report forms. Parents/caregivers will be provided with cards, which will list the most likely possible adverse events (see **Table 9**), where they can record solicited and other unsolicited events not already listed. All adverse events observed must be recorded separately and all must be reported to the IRB on IRB AE forms. All AEs regardless of severity level will be evaluated by full DSMB during scheduled meetings. The severity of adverse events will be recorded as follows:

- Mild (Grade 1): no or minimal interference with the subject's daily activity with intervention not indicated
- Moderate (Grade 2): some interference with the subject's daily activity but with intervention indicated
- Severe (Grade 3): prevents subject's daily activity and requires medical intervention
- Potentially Life Threatening (Grade 4): ER visit or hospitalization, with intervention indicated to prevent permanent impairment, persistent disability, or death
- Fatal (Grade 5): death

Based on the safety record of the yogurt, we anticipate that the following are the most likely AEs:

 Gl distress including: bloating, flatulence, nausea, emesis, anorexia, constipation and diarrhea • Allergic reactions including: anaphylaxis, hives, shortness of breath, rash, wheezing, and other reactions that the parent/caregiver or doctor believes may be related to food.

Potential symptoms relating to the existing respiratory infection (enrollment criteria/indication for antibiotics) may include: cough, earache, nasal congestion, runny nose, or sore throat. Worsening (increase in grade) or the onset of these symptoms not present at the start of the study will be reported as adverse events.

Table 9. Possible expected adverse events and grading scale.^a

Possible	Mild	Moderate	Severe	Potentially Life
Adverse Event	(Grade 1)	(Grade 2)	(Grade 3)	Threatening (Grade 4)
Loose stools	Mild symptoms causing no or minimal interference with usual social & functional activities with intervention not indicated	Moderate symptoms causing greater than minimal interference with usual social & functional activities with intervention indicated	Severe symptoms causing inability to perform usual social & functional activities with intervention or hospitalization indicated	Potentially life- threatening symptoms causing inability to perform basic self-care functions with intervention indicated to prevent permanent impairment, persistent disability, or death
Diarrhea (≥3 loose stools per day for 2 consecutive days)	Transient or intermittent episodes of unformed stools OR Increase of 3 stools over baseline per 24-hour period	Persistent episodes of unformed to watery stools OR Increase of 4 to 6 stools over baseline per 24-hour period	Increase of ≥ 7 stools per 24-hour period OR IV fluid replacement indicated	Life-threatening consequences (e.g., hypotensive shock)
Constipation	NA	Persistent constipation requiring regular use of dietary modifications, laxatives, or enemas	Obstipation with manual evacuation indicated	Life-threatening consequences (e.g., obstruction)
Fever Non-axillary (taken by armpit) temperatures only	38.0 to < 38.6°C or 100.4 to < 101.5°F	≥ 38.6 to < 39.3°C or ≥ 101.5 to < 102.7°F	≥39.3 to <40.0°C or ≥102.7 to <104.0°F	≥ 40.0°C or ≥ 104.0°F
Flatulence	Mild symptoms causing no or minimal interference with usual social & functional activities with intervention not indicated	Moderate symptoms causing greater than minimal interference with usual social & functional activities with intervention indicated	Severe symptoms causing inability to perform usual social & functional activities with intervention or hospitalization indicated	Potentially life- threatening symptoms causing inability to perform basic self-care functions with intervention indicated to prevent permanent impairment, persistent disability, or death
Lack of appetite	Mild symptoms causing no or minimal interference with usual social & functional activities with intervention not indicated	Moderate symptoms causing greater than minimal interference with usual social & functional activities with intervention indicated	Severe symptoms causing inability to perform usual social & functional activities with intervention or hospitalization indicated	Potentially life- threatening symptoms causing inability to perform basic self-care functions with intervention indicated to prevent permanent impairment, persistent disability, or death
Pain	Pain causing no or minimal interference with usual social & functional activities ^b	Pain causing greater than minimal interference with usual social & functional activities	Pain causing inability to perform usual social or functional activities	Disabling pain causing inability to perform basic self-care functions ^c OR hospitalization indicated
Rash (Cutaneous reaction)	Localized rash	Diffuse rash OR Target lesions	Diffuse rash AND Vesicles or limited number of bullae or	Extensive or generalized

			superficial ulcerations of mucous membrane limited to one site	bullous lesions OR Ulceration of mucous membrane involving two or more distinct mucosal sites OR Stevens Johnson
				syndrome OR Toxic epidermal necrolysis
Vomiting	Transient or intermittent AND No or minimal interference with oral intake	Frequent episodes with no or mild dehydration	Persistent vomiting resulting in orthostatic hypotension OR Aggressive rehydration indicated (e.g., IV fluids)	Life-threatening consequences (e.g., hypotensive shock)
Cough Earache Nasal congestion Runny nose Sore throat	Mild symptoms causing no or minimal interference with usual social & functional activities with intervention not indicated	Moderate symptoms causing greater than minimal interference with usual social & functional activities with intervention indicated	Severe symptoms causing inability to perform usual social & functional activities with intervention or hospitalization indicated	Potentially life- threatening symptoms causing inability to perform basic self-care functions with intervention indicated to prevent permanent impairment, persistent disability, or death

^a U.S. Department of Health and Human Services, National Institutes of Health, National Institute of Allergy and Infectious Diseases, Division of AIDS. Division of AIDS (DAIDS) Table for Grading the Severity of Adult and Pediatric Adverse Events, Version 2.1. [March 2017].

If any Serious AEs (SAEs) --defined as any adverse event that results in death, is life-threatening for the person involved, is likely to result in disability or permanent invalidity, results in hospitalization of a subject or prolonged hospitalization (typically Grade 3 or above – see Section 10.1.1) occur, the PI will be alerted immediately as will the IRB. If necessary, members of DSMB will be alerted immediately. The PI and/or IRB will decide if **stopping criteria** have been met. If they believe so, a teleconference will be arranged by the DSMB Administrator. The PI and Data Coordinating Center will be alerted and no more participants will be enrolled until after the meeting, which will occur within 24 hours.

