4.3 Potential Risks and Benefits

4.3.1 Potential Risks

Yogurt: Potential risks and side effects related to the probiotic cultured yogurt include: allergic reaction to drink ingredients, most likely strawberry, or digestive problems such as stomachaches or loose, watery bowels due to lactose intolerance.

There may also be side effects, other than those listed above that we cannot predict. Many side effects may go away shortly after the yogurt consumption is stopped, but in some cases side effects can be serious, long lasting or permanent.

Stool Collection: There is no known risk to stool collection. However, there may be some discomfort with collecting stool samples.

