10.1.2 Reporting Guidelines

If a parent/caregiver reports an AE/SAE that does not yet have a Date of Resolution and is continuous (no more than two days without interruption) across two follow-up periods, this AE/SAE will be considered one event. If more than two days pass between the reporting of symptoms, it will be considered as separate events. The total duration of the AE/SAE will be collected but only one AE/SAE Form will be completed for this particular event.

The following applies only for non-serious (typically below Grade 3) events; AEs of Grade 3 or above will follow the aforementioned policies for reporting and monitoring of serious adverse events

For non-serious events, if the AE has not resolved by the Day 14 follow-up, then depending on the type of AE (expected or unexpected) the research assistant will either continue to follow-up with the parent/caregiver or consider Day 14 as the final Date of Resolution:

- If the AE reported is listed on the Adverse Event Report Form (Codes 1-14) as a
 possible, expected AE, the research assistant will continue to follow-up the
 parent/caregiver a minimum of every 4 days until the AE resolves to record the Date of
 Resolution.
- If the AE reported is listed as "Other" (Code 15), or unexpected, and the Principal Investigator AND parent/caregiver considers the AE is not related/or is unlikely related to the intervention, the research assistant will not continue to follow-up past the Day 14 follow-up and will consider Day 14 as the final Date of Resolution.

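### Six of the 12 reactions that Section 10.1 names as most likely, including four of the five allergic ones, are absent from Table 9, the table it cites for the caregiver card

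*Combined protocol and SAP*

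**What the plan says.** Section 10.1 (Adverse Events) gives two accounts of what is most likely to occur.

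- The narrative list has two classes. The first is gastrointestinal "distress including: bloating, flatulence, nausea, emesis, anorexia, constipation and diarrhea". The second is "Allergic reactions including: anaphylaxis, hives, shortness of breath, rash, wheezing", followed by an open category for other reactions thought to be food-related.
- On data capture, "Parents/caregivers will be provided with cards, which will list the most likely possible adverse events", with a pointer to Table 9. The card is also the place "where they can record solicited and other unsolicited events not already listed".
- The table is headed "Table 9. Possible expected adverse events and grading scale". Rash is its only allergic-type row.

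Section 10.1.2 (Reporting Guidelines) then separates events on the adverse event form. Codes 1-14 are the possible, expected events, and a non-serious one still open at the Day 14 follow-up is followed until it resolves. Code 15 is for events that are other, "or unexpected, and the Principal Investigator AND parent/caregiver considers the AE is not related" or is unlikely to be related; for these, Day 14 is taken as the date of resolution. Events of Grade 3 or above follow the serious-event policies instead.

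Section 4.3.1 (Potential Risks) lists "allergic reaction to drink ingredients, most likely strawberry" among the yogurt risks, together with digestive problems.

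**The concern.** The narrative list and Table 9 both claim to describe the events that the sponsor expects, yet they differ most on the allergic terms. A term printed on a card is prompted. A term left off it is recorded only if a caregiver thinks to write it in or mention it. Section 11.3 plans to estimate adverse event rates with 95% confidence intervals and to compare them between groups, and safety is a stated secondary objective. If some anticipated reactions are prompted and others are not, their absolute rates are not on the same footing.

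The coding may also contradict the protocol's own expectation: a reaction that Section 10.1 calls most likely could be filed as unexpected and fall under the less complete follow-up branch of Section 10.1.2.

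Such events did occur in the sponsor's completed studies. Table 1 (adults on antibiotics, control v BB-12) shows bloating 3 of 21 v 0 of 19, breathing problems 3 of 21 v 0 of 19 and nausea 1 of 21 v 0 of 19. Table 2 (children, Days 0-10) shows one report of hives, in the BB-12 group.

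**Working it through.** No sample size or power figure is involved. The check is a count and a match.

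**Step 1: size of Table 9 against the codes.** The table has nine single-term rows (loose stools, diarrhea, constipation, fever, flatulence, lack of appetite, pain, rash, vomiting) and one row with five respiratory terms (cough, earache, nasal congestion, runny nose, sore throat). 9 + 5 = 14. Section 10.1.2 gives 14 expected codes, so the counts agree. This supports the view that the two lists are the same but does not prove it.

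**Step 2: match each named reaction to Table 9.** Emesis is read as vomiting and anorexia as lack of appetite. The open food-related category is not counted.

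| Section 10.1 term | Class | In Table 9? |
|---|---|---|
| Bloating | GI | No |
| Flatulence | GI | Yes |
| Nausea | GI | No |
| Emesis | GI | Yes (vomiting) |
| Anorexia | GI | Yes (lack of appetite) |
| Constipation | GI | Yes |
| Diarrhea | GI | Yes |
| Anaphylaxis | Allergic | No |
| Hives | Allergic | No (or under rash) |
| Shortness of breath | Allergic | No |
| Rash | Allergic | Yes |
| Wheezing | Allergic | No |

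**Step 3: proportions missing.**

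- All terms: 6/12 = 50%.
- Allergic: 4/5 = 80%.
- Gastrointestinal: 2/7 = 29%.
- With hives counted under the rash row, which Table 9 labels a cutaneous reaction: 5/12 = 42% overall and 3/5 = 60% of the allergic terms.

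**Step 4: apply Section 10.1.2.** If Codes 1-14 are the Table 9 terms, the six missing reactions take Code 15. A non-serious one still open at Day 14 is closed on that date when both the investigator and the caregiver judge it unrelated or unlikely to be related. A Table 9 term in the same position is followed to resolution.

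**The case against.** Much of the case on the other side stands.

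- **The card and form are not in the documents.** The card is described as listing the most likely events, so it could carry the narrative list rather than Table 9. The coding consequence rests on the match of 14 with 14.
- **Other routes of detection exist.** There are a call 30 minutes after the first drink, a 24-hour phone line for suspected allergic reactions, a daily diary for Days 1-14, follow-up calls on Days 7, 11 and 14 with an adverse event item, and write-in space on the card. A reader might infer that detection depends on the card; it does not. However, the diary, phone line and write-in space work best when the caregiver knows what to look for.
- **Severe reactions are covered.** Grade 3 or above follows the serious-event policies, which would be expected to include anaphylaxis. Any child with evidence of allergy stays in safety follow-up.
- **Closure at Day 14 needs two judgements.** A reaction that either the investigator or the caregiver attributes to the yogurt does not qualify.
- **The arms are treated alike.** Both yogurts contain strawberry and dairy, and the trial is double-blind with identical procedures. Under-recording at the same rate in both arms leaves the rate ratio unchanged.

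A reader might also infer that the main product risk goes unsolicited. The documents do not support that: rash is solicited, and the digestive risks in Section 4.3.1 are covered by the pain, loose stools and diarrhea rows. Nor are most of the 12 terms missing; exactly half are.

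Finally, a reader might project hives from Table 2: 1/29 × 150 = 5.2 events in the BB-12 arm. One event cannot carry that. The exact 95% interval for 1/29 is about 0.1% to 17.8%, or roughly 0.1 to 27 per 150. Table 3 lists no hives among 87 + 91 = 178 BB-12 children; pooling gives 1/(29 + 178) × 150 = 0.7, although collection methods may have differed.

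**Conclusion.** The mismatch is plain on the page: six of the 12 reactions named as most likely are not in Table 9, including four of the five allergic ones (five of 12 and three of five if hives counts as rash). That they would be unprompted depends on the card following Table 9. That they would be coded other or unexpected depends on Codes 1-14 being the Table 9 terms. Both are reasonable inferences, not facts in the documents.

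On those assumptions, the effect is limited to incomplete and uneven ascertainment and coding of Grade 1-2 hives, wheeze, shortness of breath, nausea and bloating. It bears on the absolute rates that Section 11.3 will report rather than on the comparison between arms. The documents give no sound basis for putting a number on the events lost. Even so, this is more than clerical, because safety is a stated objective and the allergic terms are the ones chiefly left out.

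**What to change.** Reconcile the Section 10.1 narrative, Table 9 and Section 10.1.2. Add anaphylaxis, hives, shortness of breath, wheezing, nausea and bloating to Table 9, the caregiver card and the adverse event form as solicited terms with their own codes. Grade them on the general severity scale already in Section 10.1, and extend the range of expected codes in Section 10.1.2 so that they are classed as expected. If hives is meant to sit under rash, say so in the table. If the card already carries the narrative list, only Table 9 and the codes need changing.

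The cost is one revision of the form, the card and the REDCap fields; Section 13.1 already provides form revision numbers. Expect slightly more minor solicited events in both arms. If children have already been enrolled, show the rates of these terms by form revision as well as overall, since recording will differ before and after the change.

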10.1.1 Serious Adverse Events

SAEs might not be related to the drink administration but are still required to be evaluated as above by the DSMB.

An SAE is any adverse event that:

- Results in death
- Is life-threatening for the person involved
- Is likely to result in disability or permanent invalidity
- Results in inpatient hospitalization or prolongation of existing hospitalization of a subject
- Results in a congenital anomaly or birth defect
- May, based on medical judgement, jeopardize the subject and may require medical intervention to prevent on the outcomes previously listed

Available from: https://rsc.tech-res.com/docs/default-source/safety/daids-ae-grading-table-mar2017.pdf

^b Usual Social & Functional Activities – Young Children: Activities that are age and culturally appropriate (e.g., social interactions, play activities, learning tasks, etc.).

^c Basic Self-care Functions – Young Children: Activities that are age and culturally appropriate (e.g., feeding self with culturally appropriate eating implement).

All AEs will be monitored by the investigator until a satisfactory resolution. In the event of SAEs, all clinical and laboratory investigations considered necessary by the investigator will continue until values have returned to normal. The investigator will provide the IRB with copies of all results of examinations and treatment carried out during follow up of SAEs. Additionally, all reports will be provided to the FDA and the NICHD Program Official.

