10.2 STOPPING CRITERIA

Drink administration may be suspended if:

- Any study participant experiences death that the DSMB believes may be related to the drink administration.
- If statistically or clinically significant amount of hospitalizations occur that the DSMB believes may be related to drink administration.
- New information from outside studies reveals that it would be unethical to continue enrolling participants in the study.
- The IRB decides that the study should be stopped.
- Any serious adverse event for which a relationship with the study product cannot be ruled out.
- The occurrence of statistically or clinically significant, similar Grade 2/moderate adverse events in the study population that the DSMB or PI believe is related to the intervention.
- A statistically or clinically significant number of severe adverse events occur in the study population.

Individuals may be withdrawn from the study for any of the following:

- Adverse events; the PI will discuss AEs with the parent/caregiver, and possibly
 with the participant's physician, as needed, to determine whether the participant
 should be withdrawn from the study.
- If parents/caregivers or participants are deemed to be non-cooperative (e.g. refuse to collect stools, participate in follow-up calls or fail to complete diaries).
- If parent/caregiver is lost to follow-up, i.e. more than 1 week without contact with study personnel during the follow-up period.
- Serious adverse events related to drink administration, as determined by PI, parent/caregiver or participant's primary care physician.

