10.3 Safety Oversight

The Data Safety Monitoring Board, DSMB, will function as an independent oversight committee charged with overseeing participant safety and providing recommendations to the PI and Georgetown University regarding the continuing conduct of the study. The DSMB will review periodic blinded Interim Safety Reports. Additionally, unblinded but sealed Interim Safety Reports will be provided to each voting DSMB member should the committee determine that review of unblinded safety data is warranted.

The DSMB is responsible for monitoring the tolerability, safety and effectiveness of the yogurt. They will meet periodically once the first participant is enrolled and continue to do so as long as participants are actively involved in the study. One meeting will occur before enrollment to review study objectives, data collection and safety measures. Meetings will occur via teleconferences or at Georgetown University.

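### After a serious adverse event, prompt DSMB review depends on a PI and/or IRB decision, although two of the seven stopping criteria turn on the DSMB's own belief

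*Combined protocol and SAP*

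**What the plan says.** Section 10.1 of the combined protocol and SAP sets the SAE procedure. The PI and the IRB are alerted immediately. For the DSMB the text reads "If necessary, members of DSMB will be alerted immediately. The PI and/or IRB will decide if" the stopping criteria "have been met. If they believe so, a teleconference will be arranged by the DSMB Administrator". The PI and the Data Coordinating Center are then alerted, and "no more participants will be enrolled until after the meeting, which will occur within 24 hours". No rule says when alerting the DSMB is necessary.

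Section 10.1.1 adds: "SAEs might not be related to the drink administration but are still required to be evaluated as above by the DSMB".

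Section 10.2 lists seven grounds for suspending drink administration. The first is "Any study participant experiences death that the DSMB believes may be related to the drink administration". The second is "If statistically or clinically significant amount of hospitalizations occur that the DSMB believes may be related to drink administration".

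Section 10.3 makes the DSMB the independent safety committee. On frequency it says only "They will meet periodically once the first participant is enrolled". It also provides that "unblinded but sealed Interim Safety Reports will be provided to each voting DSMB member", to be opened if the committee decides that unblinded review is warranted. Section 10.1 separately has the full DSMB evaluate all adverse events, of any severity, at its scheduled meetings.

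**The concern.** The order of decisions in 10.1 does not match the wording of 10.2. Under 10.1, the PI and/or IRB first decide that a criterion is met, and the DSMB is convened afterwards. Under 10.2, the death and hospitalization criteria are met only through the DSMB's own judgement that the product may be responsible. The body that must form the belief is therefore called only after others have decided the matter.

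Death and hospitalization are the events for which an independent committee matters most, and the participants are children aged 3 to 12. If the PI and IRB both judge such an event not to meet any criterion, the DSMB need not hear of it until its next scheduled meeting, and enrolment continues. What is at stake is independence and timeliness. No endpoint, alpha level or power figure is affected.

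**Working it through.** The point concerns who decides, so the check is a side-by-side reading, followed by a workload estimate for the fix.

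**1. Who judges each study-level criterion in 10.2**

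| Criterion | Judge named in 10.2 |
|---|---|
| Related death | DSMB |
| Related hospitalizations | DSMB |
| New outside information | none |
| IRB decision to stop | IRB |
| SAE whose relationship cannot be excluded | none |
| Similar Grade 2 events | DSMB or PI |
| Number of severe events | none |

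Count: DSMB alone 2, DSMB or PI 1, IRB 1, none named 3; total 2 + 1 + 1 + 3 = 7. Section 10.1 names the PI and/or IRB as deciders for all of them. It conflicts with 10.2 on two of the seven.

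**2. Routes by which an SAE reaches the DSMB**

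- Immediate alert: discretionary, with no stated trigger. An alert is also not a meeting.
- Teleconference within 24 hours, with enrolment paused: only after a PI and/or IRB decision.
- Scheduled meeting: unconditional, but no interval is stated.
- Section 10.1.1: requires DSMB evaluation, but refers back to the procedure above it and sets no deadline.

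The only unconditional route is the scheduled meeting.

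**3. What happens to a death or hospitalization**

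Both are SAEs by definition. If a relationship cannot be excluded, the fifth criterion applies. It names no judge, so the PI or IRB can apply it and convene the DSMB without any prior DSMB belief. The gap is therefore confined to SAEs for which the PI and IRB both decide that no criterion is met.

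**4. Workload if every SAE is copied to the DSMB chair**

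- Input: 3 SAEs among 60 children (29 on BB-12, 31 on control) in the Phase 1 pediatric study, followed to day 180 (4.1.9, Table 2). Three different children are assumed.
- Rate: 3/60 = 5.0%; exact (Clopper-Pearson) 95% CI 1.04% to 13.92%.
- Over 300 children: 300 × 0.050 = 15; interval 300 × 0.0104 = 3.1 to 300 × 0.1392 = 41.8, so about 3 to 42.
- Sensitivity: one of the three was a Grade 4 fever. Without it, 2/60 = 3.3% (0.41% to 11.53%), which gives 10 reports (1 to 35).

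The Phase 1 children were aged 1 to 5 and were not selected for antibiotic use, so this is a guide to workload only.

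**The case against.** The strongest reply is that the ordinary reading of 10.1 has two steps: the PI or IRB makes a preliminary call, and the DSMB then decides. Several safeguards surround that step. The fifth criterion catches any SAE whose relationship cannot be excluded. The IRB is told of every SAE, can trigger the meeting without the PI, and can stop the study outright. SAE reports go to the FDA and the NICHD Program Official. The DSMB sees everything at scheduled meetings, which can be read as satisfying 10.1.1. All of this stands, and it rules out four stronger readings.

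- *The procedure is circular, so the DSMB can never be convened for a death or hospitalization.* It can be, through the fifth criterion.
- *The PI can veto DSMB review.* The and/or wording also lets the IRB act alone, so an SAE must be screened out by both. Nor is the sentence alerting the PI clearly a drafting slip, since it fits a call triggered by the IRB.
- *A blinded PI lacks by-arm data, so the DSMB chair would decide better.* Under 10.3 the sealed reports are opened only if the committee so decides. A chair screening one SAE would see the same blinded report. The gain is independence, not by-arm data.
- *A known number of children enrol before the DSMB looks.* With an assumed interval of 3 to 12 months, 75 a year (section 6) gives 75/12 × 3 = 19 to 75 children, and 300 over 42 months (11.3) gives 300/42 × 3 = 21 to 86. The interval is not in the documents. These figures are also not what a fix would save, because enrolment also continues after an SAE that the chair screens out. The relevant cases are those in which the chair would call a meeting and neither the PI nor the IRB would. Nothing in the documents gives their frequency.

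What the reply does not remove is the gate itself. The safeguards either depend on the same PI or IRB judgement, or wait for a meeting at an unstated interval.

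**Conclusion.** The point holds as a misplaced decision step. For an SAE that the PI and IRB both screen out, the plan gives no prompt, independent DSMB review, even though two of the seven suspension criteria rest on the DSMB's belief. Scheduled DSMB review still takes place, so the loss is of time and independence, not of review itself.

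The size in children exposed cannot be estimated from the documents. The conclusion rests on the text alone; it assumes only that the DSMB charter, which is not among the documents, does not already supply a faster route. Severity is minor to moderate, and the change is a cheap improvement.

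**What to change.** In 10.1, replace the text that starts at "If necessary, members of DSMB will be alerted immediately. The PI and/or IRB will decide if" and runs to the end of "have been met. If they believe so, a teleconference will be arranged by the DSMB Administrator" with:

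> *Each event meeting the 10.1.1 definition is sent to the DSMB chair at the same time as to the IRB. The DSMB chair, the PI or the IRB may each call a DSMB teleconference if a 10.2 criterion may have been met; the DSMB judges the criteria that depend on its belief.*

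Keep the next sentence, on the enrolment pause and the 24-hour meeting. Leave 10.1.2 unchanged, so that events of Grade 3 or above still follow SAE reporting to the PI and IRB. The sealed reports in 10.3, and the committee's discretion to open them, also stay as they are.

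Cost: one edit in 10.1, about 15 SAE reports (95% CI 3 to 42) copied to the chair over the trial, and possibly a few more short enrolment pauses. It adds no tables and no efficacy look, and it changes neither alpha nor power.
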